#### 1. Hypothesis / Objective / Goals / Aims.

Briefly describe the study's hypothesis / objectives / goals / aims.

Placebo interventions offer a cost-effective and scalable tool in helping people manage a host of psychological and physical conditions. However, the prevalent idea that people need to be deceived into believing they are taking an active treatment in order for placebos to work prevents their widespread use. Fortunately, accumulating research suggests that placebos can still produce beneficial effects even when administered without deception (i.e., non-deceptive placebos) by communicating to people what placebos are, explaining the science behind how they work, and highlighting how they can still be effective even if people know they are taking them.

Goal:

Building on this research, the goal of this project is to harness the beneficial effects of placebos administered without deception by testing the efficacy of a cost-effective, easily implementable, and scalable telehealth interventions for helping people manage their stress and anxiety related to the COVID-19 pandemic. The intervention involves participants watching an informational video on the beneficial effects of placebos without deception, remotely interacting with an experimenter, and taking open-label placebo pills (NDP Video + Experimenter). The intervention will be compared to a no treatment, assessment only control group.

Prediction:

We expect those in the NDP Video + Experimenter group to experience less overall stress and anxiety related to COVID-19 compared to the NT Control group.

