Our assumption of a d effect size of .60 is a liberal assumption based on the literature in which the d effect size between a non-deceptive placebo and a no treatment control ranges from .30 to 1.00. The most relevant non-deceptive placebo study is El Brihi et al. (2019) in which they tested the effects of non-deceptive placebos on emotional distress and positive mental well-being. Comparing two types of non-deceptive placebos versus a control showed a non-deceptive placebo effect that ranges from a Cohen's d of .78 to 1.01 on emotional distress. Comparing two types of non-deceptive placebos versus a control showed a non-deceptive placebo effect that ranges from a Cohen's d of .55 to .93 for psychological well-being. As such, we estimate that a d effect size of .60 between a control group and our non-deceptive placebo group because our primary outcomes is also emotional distress and psychological well-being. A .60 d effect size is within a reasonable range of what is expected regarding a non-deceptive placebo effect on emotional distress. This will allow us to run approximately 50 in each condition, which is more than the sample size of the El Brihi et al. (2019) study in which they had n = 29 in the control condition and n = 30 and n = 31 in each of the non-deceptive placebo condition.

For our primary outcomes, we plan to run a 2 (Group) by 3 (Time: Time 2, Time 3) mixed factorial ANOVA (while controlling for baseline levels) followed by independent pairwise comparisons at each of time point. When possible, we plan to use multiple imputation methods to account for missing data. If a participant is missing data from 2 or more time points for our primary outcome, they will be removed for analyses. If a person is unresponsive for 5 days, we will consider them a dropout. We will send a final letter indicating that we apologize for their drop

and that they can contact us if they need anything and provide them resources if they require it. If participants wants to drop out, we can inquire why and offer them resources and contact information for future studies.

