**11. Screening, Recruitment, and Determining Eligibility.**

**11A. Describe how subjects will be identified and recruited, including who will perform the recruitment.**

Broadly, our target sample is any Michigan resident that fits our eligibility criteria. Participants will be between 18 and 30, English as their primary language, do not have a self-reported history of severe mental illness, do not have a current diagnosis of COVID-19, no major health problems such as heart and lung diseases, and is able and willing to participate in a longitudinal study spanning 17 to 20 days. In order to ensure people's identity, people will be required to show their ID in a HIPPA compliant Zoom call. In order to ensure that our sample is currently experiencing a moderate amount of stress and anxiety related to COVID-19, we will also only enroll participants who score a 35 or higher on the COVID Stress Scale.

For those in the intervention condition, we will have additional criteria asking if they would be willing to provide an address where we can send them a bottle of placebo pills and if they are willing to take placebo pills 2 weeks. People in the intervention group will also indicate that they are willing to take pills for 2 weeks and not be allergic to common ingredients found in pills such as microcrystalline cellulose, silica, gelatin, titanium dioxide, Red # 3, and Blue #1.

Participants will be recruited from the MSU student population and broader Michigan community. Since the study is online, we are not restricted by East Lansing geography. We plan to recruit online through Craigslist, Facebook, and other research online platforms such as ResearchMatch.

We will also recruit through the Paid Subject Pool from the Communication Arts and Sciences Department that is managed by [name].

We are also partnering with a collaborator from University of Michigan to help with recruitment, and we plan to use their health research participant pool. The collaborator will not interact or intervene with subjects for research purposes, they will not collect data or obtain consent or study or analyze any of the data with identifiable information. The University of Michigan IRB will

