Clinical Trial Statistical Analysis Plan

Title: Effects of Open-label Placebos Administered Through Telehealth on COVID-related Stress, Anxiety, and Depression

Brief Title: Effects of Open-label Placebos on COVID-related Psychological Health

Study Sponsor: Michigan State University

Principle Investigator:

Name: [name]

Official Title: Professor of Psychology

Affiliation: Michigan State University

[contact]

Email: [contact]

NCT Number: NCT05035550

Version Date: 1.22.21

Statistical Analysis Plan

All analyses were conducted on SPSS version 26 (IBM, Armonk, NY). Prior to our primary analyses, we first interpolated missing data using a maximum likelihood estimation (MLE). Second, we conducted an independent sample t-test on baseline measures of each primary outcome measure to ensure that the control and open-label placebo group did not differ prior to the administration of the intervention.

The primary outcomes at the endpoint (reduction in COVID stress, perceived stress, anxiety, and depression) were calculated using change from baseline scores (endpoint minus baseline) with positive numbers indicating greater reduction in symptoms at endpoint. First, each primary outcome was submitted to a one-way analysis of covariance (ANCOVA), with group as the independent variable and the mean baseline score for each outcome measure submitted as a covariate to control for variability in baseline scores (Lembo et al., 2021; Van Breukelen, 2006). We reported outlier detection procedures and additional robust analyses in the Supplementary Materials. Effect sizes for pairwise comparisons were calculated using Cohen's d. Secondary outcomes were analyzed using descriptive statistics and t-tests. All significance tests were analyzed at $p = .05$.

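### Four primary outcomes are each tested at .05, and neither document says what counts as success across them

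*SAP*

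**What the plan says.** The SAP gives four primary outcomes equal standing: "The primary outcomes at the endpoint (reduction in COVID stress, perceived stress, anxiety, and depression) were calculated using change from baseline scores". It then states that "each primary outcome was submitted to a one-way analysis of covariance (ANCOVA") with group as the factor and baseline as covariate, so there are four separate primary tests. On the threshold it says only "All significance tests were analyzed at" p = .05. It contains no adjustment, testing order, composite or success rule. The Supplementary Materials are mentioned only for outlier procedures and robust analyses.

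The protocol does not fill the gap. Section 9B sizes the trial for a single comparison at an alpha of .05. Its missing-data rule refers to a primary outcome in the singular without identifying it.

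The SAP is in the past tense ("All analyses were conducted on SPSS version 26"), which suggests that the analyses were complete when it was written.

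**The concern.** Calling four outcomes primary gives the investigators four chances at a primary finding. The plan does not limit what may be concluded if, say, anxiety alone reaches p < .05. A reader who takes that result as evidence that the intervention works is relying on an error rate that the plan neither states nor controls. What is at stake is the strength of evidence behind any headline claim that rests on one or two of the four outcomes.

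**Working it through.** **Inputs.** From the SAP: four primary outcomes, one test each, .05 per test. From protocol section 9B: d = .60, power .80, alpha .05, at least 50 and at most 200 per arm, and d = .30 at the maximum. Assumed, because neither document says: two-sided tests, equal correlation ρ between the four test statistics, and correlation r between baseline and endpoint.

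**The plan's own sample size.** With the noncentral t, d = .60 at two-sided .05 needs 45 per arm for 80% power. At 50 per arm, power is .844. The stated 50 is therefore on the safe side. It equals 45/.90, so an unstated 10% dropout allowance would explain it. This does not affect the multiplicity question.

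**Chance of at least one false positive, all four outcomes null.**
- If independent, two-sided: 1 − .95⁴ = 1 − .8145 = .1855.
- If independent, favourable direction only: 1 − .975⁴ = 1 − .9037 = .0963.
- If correlated, two-sided: 1 − ∫[Φ((c − √ρ·u)/√(1−ρ)) − Φ((−c − √ρ·u)/√(1−ρ))]⁴ φ(u) du, with c = 1.96. For the favourable direction, drop the second Φ term.

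| ρ (assumed) | Any one, two-sided | Any one, favourable | Holm, two-sided |
|---|---|---|---|
| 0 | 18.5% | 9.6% | 4.9% |
| .5 | 15.6% | 7.8% | 4.3% |
| .7 | 13.0% | 6.5% | 3.7% |
| .9 | 9.4% | 4.7% | 2.6% |

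The single-test references are 5% two-sided and 2.5% favourable. The Holm column uses c for .05/4 = .0125, because under the global null Holm makes an error only if its first step rejects.

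**If all four had to succeed.** The all-null case does not settle this, because the error rate is higher when some outcomes respond. Take three outcomes effective at d = .60 with 50 per arm, one null, and independence. The chance that all four reach .05 is about .05 × .844³ = .030 at r = 0, and .05 × .929³ = .040 at r = .5. As power for the effective outcomes approaches 1 it approaches .05 and cannot exceed it, since the null outcome must itself be rejected at .05. That bound holds at any correlation, so an all-four rule needs no adjustment.

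**Power under Holm.** The noncentrality is d/√(1−r²) × √(n/2). At n = 50 and d = .60 it is .60 × 5 = 3.00 for r = 0, and (.60/.866) × 5 = 3.46 for r = .5.

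| Setting | Power at .05, r = 0 to .5 | Power at .0125, r = 0 to .5 |
|---|---|---|
| 50 per arm, d = .60 | .84 to .93 | .68 to .82 |
| 200 per arm, d = .30 | .85 to .93 | .69 to .83 |

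The .0125 column is Holm's first step, which is its worst case. If all four outcomes respond at d = .60 with 50 per arm, simulated per-outcome power under Holm is .74 to .77 (r = 0) or .87 to .90 (r = .5), for ρ from .9 to .3.

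**The case against.** The strongest reply is that the SAP never says one significant outcome is enough. The four tests can be read as four separate claims, each reported on its own result and each with a 5% error rate. On that reading nothing is inflated, and whether to control error across the family is partly a matter of judgement. This stands as a limit on the point: the inflated figures belong to the any-one reading only. It does not close the gap, because all four outcomes are called primary and nothing restricts what may be concluded from one of them.

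A second reply is that the inflation is modest. The protocol's prediction is directional and four distress scales should correlate well, so the lower rows of the favourable column are the more realistic ones. That is fair, but even 4.7% is nearly twice 2.5%.

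A third reply is that COVID stress is the implied lead outcome. Protocol section 1 expects the intervention group "to experience less overall stress and anxiety related to COVID-19", and section 11A says "we will also only enroll participants who score a 35 or higher on the COVID Stress Scale". A reader might infer a ranking from these. The first names constructs and the second is an eligibility rule. Neither designates a lead outcome, and the SAP does not rank the four.

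**Conclusion.** The gap is real and worth fixing. Four outcomes are primary, each is tested at .05, and neither document states an adjustment, a lead outcome or a success rule. On the any-one reading, the false-positive chance under the global null is about 9% to 19% two-sided, or 4.7% to 9.6% in the favourable direction, for assumed correlations of .9 to 0.

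Two stronger conclusions do not follow. A reader might say that the trial has a 19% false-positive rate. That requires both the any-one rule, which is not written, and independence, which is unlikely for these scales. A reader might also fold in the differences between the two documents. Protocol section 9B describes the primary outcomes differently ("because our primary outcomes is also emotional distress and psychological well-being") and plans another model ("we plan to run a 2 (Group) by 3 (Time: Time 2, Time 3) mixed factorial ANOVA"), where the SAP omits well-being and uses an endpoint ANCOVA. Those passages need reconciling, but that is a separate matter and contributes nothing to the figures here.

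**What to change.** **If the analyses are done, as the SAP's tense suggests:** report Holm-adjusted p-values for the four primary outcomes (family-wise two-sided .05) beside the unadjusted ones. Claim only Holm-significant outcomes as primary findings, and disclose that the adjustment was added afterwards. This needs no new data.

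**If they are not done:** replace the .05 sentence for the primary family with wording such as: *The four primary outcomes are tested with Holm's procedure at a two-sided family-wise .05; only Holm-significant outcomes are claimed as primary findings.*

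**If a lead outcome or an all-four rule was documented before the data were seen:** state that rule instead. Holm is suggested because it avoids choosing a lead outcome after the fact.

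**Cost.** The cost is power, as tabulated above. To keep 80% at Holm's first step, d = .60 needs 64 per arm (r = 0) or 49 (r = .5). For d = .30 the figures are 250 or 188, and 250 exceeds the protocol's maximum of 200. These sizes overstate the cost when several outcomes respond. An all-four rule needs no adjustment but also loses power: at 50 per arm with all four effects at d = .60, the chance of winning all four is .57 to .76 (r = 0) or .78 to .88 (r = .5), for ρ from .3 to .9.
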